3.3 SELECTION OF TRIAL POPULATION

It is anticipated that approximately 40 patients with AD from the parent trial 1368-0032 will be eligible for enrolment in this extension trial. This extension trial will utilize the same sites from the parent trial across the same countries.

A log of all patients enrolled into the trial (i.e. who have signed informed consent) will be maintained in the Investigator Site File (ISF) irrespective of whether they have been treated with investigational drug or not.

If a patient is enrolled in error (does not meet all inclusion criteria or meets one or more exclusion criteria on the day of enrolment), the sponsor should be contacted immediately.

3.3.1 Main diagnosis for trial entry

Patients with AD will be included in this trial if they fulfil all the inclusion and do not present any of the exclusion criteria.

Patients who prematurely discontinued blinded treatment (up to Week 16) in the parent trial (1368-0032) are not eligible for this study. In addition patients from 1368-0032 must have

shown a response in order to be eligible. Patients from the 1368-0032 who were in the non-responder category at week 16, which was defined as less than EASI 75, must have completed the EOS visit and must attain at least an EASI 50 by the last infusion of BI 655130 (Week 28) or by the EOS in order to be eligible for this extension trial.

Patients from the 1368-0032 who were in the responder category at week 16 (V7) which was defined as an EASI 75 or greater, are eligible as long as they have completed the (EOS) visit. If this patient drops to an EASI 50 score prior to the planned EOS at Week 28, they will immediately perform EOS in 1368-0032 and enter into this extension trial.

Patients should enrol into the extension trial as soon as possible after conclusion of the parent trial. It is preferred that the end of study (EOS) visit from parent trial (1368-0032) will be combined with Visit 1 of this trial which includes the first SC dose of trial drug. The Sponsor must be notified if enrolment is delayed. Patients must be enrolled within a maximum of 12 weeks after the EOS visit from 1368-0032. (Refer to [Section 6.2.1](#) for more detailed information on study procedures).

The results of the safety labs as well as Infection Testing will be available/reported after the patient has entered and received the first dose of study medication in this trial. Refer to [Section 3.3.4.1](#) for discontinuation of treatment rules.

Please refer to [Section 8.3.1](#) (Source Documents) for the documentation requirements pertaining to the in- and exclusion criteria.

3.3.2 Inclusion criteria

1. Signed and dated written informed consent in accordance with Good Clinical Practice (GCP) and local legislation prior to the start of any screening procedures
2. Patients who completed the 1368-0032 trial and did not prematurely discontinue treatment prior to week 16, and;
In the 1368-0032 re-allocation period (V7 to V11):
 - If an original non-responder from week 16 (V7), attained at least EASI 50 by last infusion (week 28) or by the EOS.
 - If an original responder from week 16 (V7) completed the last visit Week 28 (EOS) or dropped to a EASI 50 score prior to Week 28.
3. Women of childbearing potential (WOCBP)¹ must be ready and able to use highly effective methods of birth control per ICH M3 (R2) that result in a low failure rate of less than 1% per year when used consistently and correctly for the duration of the trial and 16 weeks after last study drug administration. A list of contraception methods meeting these criteria is provided in the patient information. (Refer to [Section 4.2.2.3](#))

¹A woman is considered of childbearing potential (WOCBP), i.e. fertile, following menarche and until becoming post-menopausal unless permanently sterile.

Permanent sterilisation methods include hysterectomy, bilateral salpingectomy and bilateral oophorectomy.

Tubal ligation is NOT a method of permanent sterilisation.

A postmenopausal state is defined as no menses for 12 months without an alternative medical cause.

3.3.3 Exclusion Criteria

1. Women who are pregnant, nursing, or who plan to become pregnant while in the trial. Refer to [Section 4.2.2.3](#)
2. Any new documented active or suspected malignancy except appropriately treated basal cell carcinoma, squamous cell carcinoma of the skin or in situ carcinoma of uterine cervix.
3. Use of any restricted medication as specified in [Section 4.2.2.1](#) or any drug considered likely to interfere with the safe conduct of the study, as assessed by the investigator.
4. Active systemic infections during the last two weeks prior to first drug administration. Refer to [Section 1.4.2](#) and [Section 4.2.1](#)
5. Currently enrolled in another investigational device or drug trial, except for 1368-0032.
6. Any condition which would prevent the patient continuing on treatment in this trial 1368-0037.
7. Evidence of a current or previous disease, medical condition (including chronic alcohol or drug abuse or any condition) other than AD, surgical procedure, psychiatric or social problems, medical examination finding (including vital signs and ECG), or laboratory value at the screening outside the reference range that in the opinion of the investigator is clinically significant and would make the study participant unreliable to adhere to the protocol, comply with all study visits/procedures or to complete the trial, compromise the safety of the patient or compromise the quality of the data.
8. History of allergy/hypersensitivity to the systemically administered trial medication agent or its excipients.

3.3.4 Withdrawal of patients from treatment or assessments

Patients may discontinue trial treatment or withdraw consent to trial participation as a whole (“withdrawal of consent”) with very different implications; please see [Section 3.3.4.1](#) and [Section 3.3.4.2](#).

Every effort should be made to keep the patients in the trial.

Measures to control the withdrawal rate include careful patient selection, appropriate explanation of the trial requirements and procedures prior to trial enrolment, as well as the explanation of the consequences of withdrawal.

The decision to discontinue trial treatment or withdraw consent to trial participation and the reason must be documented in the patient files and Electronic Case Report Form (eCRF). If the reason for discontinuation is death, this should be reported on the SAE form as well, regardless of causal relationship.

3.3.4.1 Discontinuation of trial treatment

An individual patient will discontinue trial treatment if:

- The patient wants to discontinue trial treatment, without the need to justify the decision.
- The patient has repeatedly shown to be non-compliant with important trial procedures and, in the opinion of both, the investigator and sponsor representative, is not willing or able to adhere to the trial requirements in the future.
- The patient misses more than 3 consecutive doses of trial treatment.
- The patient is unable to discontinue use of a restricted medication ([Section 4.2.2.1](#)) or requires other concomitant therapy that in the opinion of the investigator may interfere with trial treatment.
- The patient requires rescue medication for the treatment of unstable or worsening of AD. Refer to [Section 4.2.2.1](#)
- The patient can no longer receive trial treatment for medical reasons (such as surgery, adverse events, and other diseases.) For individual stopping rules related to specific adverse events, please see [Section 4.2.1](#) other treatments and emergency procedures.
- Malignancies during the trial. Refer to [Section 4.2.1](#)
- Severe, progressive, or uncontrolled hepatic disease during trial.
- The patient becomes pregnant during the trial.
- Confirmed active tuberculosis during the trial.
- The patient tests positive for HIV or Hepatitis B or C during the trial.

If a patient permanently discontinues trial treatment, the patient should return for the end of treatment (EOT) procedures as well as the end of study (EOS) procedures as outlined in the [Flow Chart](#) and [Section 6.2.3](#).

Discontinuation due to pregnancy

If a patient becomes pregnant during the trial the investigator must follow the AE reporting procedure as noted in [Section 5.2.6.2.3](#). The patient must discontinue drug and perform EOT and EOS procedures accordingly. The patient will be followed up until birth or otherwise termination of the pregnancy.

The data of the patient will be collected and reported in the clinical trial report (CTR) until last patient last visit (LPLV) and that any events thereafter will be reported in the BI Pharmacovigilance database.

It is per the Investigator opinion and judgment when trial medication can be temporarily interrupted and then reinstated for certain medical reasons such as surgery, adverse events

and other diseases. In these cases of a temporary discontinuation/interruption of trial treatment, trial treatment should be restarted as soon as medically justified. (Refer to [Section 4.1.4](#) and [Section 4.2.1](#)).

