4.2 OTHER TREATMENTS, EMERGENCY PROCEDURES, RESTRICTIONS

4.2.1 Other treatments and emergency procedures

Stable doses of concomitant therapies for chronic conditions, for which neither the condition nor the treatment are judged to exclude the patient from participation are permissible. All concomitant medications should be carefully evaluated by the investigator and the Clinical Trial Manager should be contacted when there are questions regarding concomitant medications.

During the trial, if the severity and progression of the patients' AD worsens the investigator can treat the patient with rescue treatment i.e. Standard of Care (SoC) of his/her choice. The sponsor will not provide/supply SoC treatment(s) to the sites. Refer also to [Section 4.2.2.1](#).

Patients with active systemic infections during the parent 655130 study must delay Visit 1 in this study until the infection has resolved for at least 2 weeks.

Severe infections according to Rheumatology Common Toxicity Criteria (RCTC) grading, serious infections, and opportunistic or mycobacterium tuberculosis infections:

Treatment of the infection should be initiated promptly according to local SoC. No further trial medication should be administered until the active infection has resolved.

Treatment with BI 655130 may be restarted when the patient has recovered according to investigator's assessment.

Malignancies

In case of occurrence of malignant neoplasm other than appropriately treated basal cell carcinoma or squamous cell carcinoma of the skin or in situ carcinoma of uterine cervix, the investigator should discontinue treatment with the trial medication, and notify the Clinical Trial Manager (CT Manager). Diagnostics and treatment should be initiated according to local SoC.

Systemic Hypersensitivity including anaphylactic reaction

In case of systemic hypersensitivity including anaphylactic reaction emerging during or after injection(s) of trial medication, the investigator should consider in accordance with severity of the reaction and local SoC to

1. Stop further injection(s)
2. Treat with systemic anti-histamines, i.v. steroids, and in case of a severe allergic reaction (e.g., anaphylactic reaction) epinephrine

Also draw a plasma sample for IgE and Antidrug antibodies (ADA) as detailed in the laboratory manual and consider the evaluation of histamine, serum tryptase, and complement components.

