Information on clinically significant previous and concomitant illnesses, other than AD, or any clinically significant signs or symptoms that are present before informed consent, or pre-existing conditions identified through findings from assessments and examinations done during Visit 1 will be recorded as medical and surgical history.

All ongoing AEs/SAEs at the end of the parent trial will be recorded on the Baseline Condition eCRF page of this 1368-0037 study.

Height and Weight

Height and Weight will be collected and reported in the eCRF per the [Flow Chart](#).

Smoking Status

Smoking status will be collected at and reported in the eCRF per the [Flow Chart](#).

Infection screening:

Infection testing will include tuberculosis, hepatitis B, hepatitis C, and HIV assessments (see [Table 5.2.3:1](#)). The results of the Infection Testing will not be available until after the patient receives the first dose at Visit 1. See [Section 3.3.4.1](#) for Discontinuation Rules.

If there is less than 12 week gap from the EOS of the preceding trial to V1 of this trial, the Infection testing does not have to be repeated at Visit 1.

QuantiFERON TB testing

Patients with suspected false positive or indeterminate QuantiFERON TB result may have the test repeated once. If after repeat testing the QuantiFERON TB result is “indeterminate” A PPD skin test may be performed locally. A tuberculin skin test reaction $\geq 10\text{mm}$ ($\geq 5\text{mm}$ if receiving $\geq 15\text{mg/d}$ prednisone or its equivalent) is considered positive.

Patients who now test positive for QuantiFERON TB test may continue and receive treatment in this study if further work up (according to local practice/guidelines) establishes conclusively that the patient has no evidence of active tuberculosis.

If presence of latent tuberculosis is established, patients can receive anti-tuberculosis treatment (according to local practice/guidelines) and continue receiving study medication.

Pregnancy Testing

Urine pregnancy testing for all woman of childbearing potential will be conducted on-site prior to every dosing and must be negative to receive study drug. A positive urine test must be confirmed with a serum pregnancy test at the central laboratory

Concomitant medication review:

Any concomitant treatment taken since the last visit of previous study will be recorded in the eCRF.

Review of inclusion/exclusion criteria:

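### Protocol 3.3.4.1 requires patients with confirmed active tuberculosis to stop treatment, but 4.2.1 allows restart after a tuberculosis infection, and neither section is given precedence

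*Protocol*

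**What the plan says.** Protocol Section 3.3.4.1 lists the conditions under which a patient will discontinue trial treatment. One is "Confirmed active tuberculosis during the trial", with no exception or restart provision attached. The separate bullet on medical reasons adds "For individual stopping rules related to specific adverse events, please see" and names Section 4.2.1. Another bullet ends treatment when "The patient misses more than 3 consecutive doses of trial treatment".

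Section 4.2.1 has one paragraph for severe infections, serious infections and "opportunistic or mycobacterium tuberculosis infections". After prompt treatment by local standard of care, its rule is "No further trial medication should be administered until the active infection has resolved", followed by "Treatment with BI 655130 may be restarted when the patient has recovered" in the investigator's assessment. For malignancies (certain treated skin and cervical lesions aside), the same section says the "investigator should discontinue treatment with the trial medication".

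Section 6.2.1 deals with tuberculosis testing. A patient who newly tests positive may continue if further work-up "establishes conclusively that the patient has no evidence of active tuberculosis". A patient with latent disease can be treated for it and stay on study drug.

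**The concern.** The two sections give different instructions for the same event. Under 3.3.4.1 active tuberculosis ends treatment. Under 4.2.1 it pauses treatment, and the investigator decides when to resume. The protocol states no order of precedence.

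A site that stops permanently breaches neither section, because 4.2.1 only permits restart. The risk therefore runs one way, towards re-dosing an immunomodulator after active tuberculosis. The rule is also likely to be consulted in practice. Infection results come back only after the first dose, and Sections 3.3.1 and 6.2.1 both point to 3.3.4.1 for what to do then. The Year 1 flow chart repeats infection testing at Week 48, and treatment is planned for about four years.

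**Working it through.** The main check is a comparison of texts; the arithmetic only sets the size.

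**Instructions side by side**

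| Situation | Section | Instruction |
|---|---|---|
| Confirmed active tuberculosis | 3.3.4.1 | Discontinue; EOT and EOS procedures follow |
| Tuberculosis infection, active | 4.2.1 | Hold until resolved; restart allowed |
| Positive test, active disease excluded | 6.2.1 | May continue |
| Latent tuberculosis | 6.2.1 | Treat and continue study drug |
| Malignancy | 3.3.4.1 and 4.2.1 | Discontinue in both (listed exceptions in 4.2.1), with a cross-reference |

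**Can the first two rows be reconciled?**

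1. *4.2.1 covers latent disease only.* No. It ties the hold to the active infection resolving, and 6.2.1 already keeps latent cases on drug without a hold.
2. *Discontinuation in 3.3.4.1 is temporary.* No. The bullet sits with pregnancy, malignancy and positive HIV or hepatitis tests. Temporary interruption has its own general paragraph at the end of that section, which does not mention tuberculosis.
3. *The missed-dose rule settles it.* Only in part; see the first calculation.

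**How long a hold still permits restart**

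Inputs: dosing every 4 weeks (28 days) and a visit window of ±14 days (flow chart); discontinuation after more than 3 consecutive missed doses (3.3.4.1).

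- Days between given doses with 3 missed: (3 + 1) × 28 = 112 days = 16 weeks.
- If the last dose is 14 days early and the restart dose 14 days late: 112 + 2 × 14 = 140 days = 20 weeks.

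A fourth consecutive missed dose forces discontinuation. The documents do not say how long treatment of active tuberculosis lasts, and 4.2.1 ties restart to the investigator's view of recovery, not to completing therapy.

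**Effect on the efficacy analysis**

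Inputs: about 40 patients, no more than 45 (Protocol 7.5). For binary efficacy endpoints, data after premature discontinuation are treated as missing beyond the last dose plus 4 weeks (SAP 6.6.2). Continuous endpoints use observed data.

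- One patient reclassified: 1/40 = 2.5 percentage points; 1/45 = 2.2 points.
- Week 48 is affected only if last dose + 4 < 48, so last dose < Week 44. On the 4-weekly schedule the latest such dose is Week 40.

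**Effect on the primary endpoint**

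Under Protocol 7.2.5 any adverse event from first dose to the end of the residual effect period is treatment-emergent. On-treatment tuberculosis counts the patient once, whether drug is stopped or restarted.

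**The case against.** The strongest reply is that the sections can coexist. Section 3.3.4.1 is mandatory and specific to one confirmed diagnosis. Section 4.2.1 is permissive and covers a broad class of infections, so it need not override the stricter rule, and it could still govern a hold while suspected tuberculosis is investigated. That is a fair reading, and 6.2.1 leans the same way. But a site has to infer it: 4.2.1 names tuberculosis, speaks of active infection and makes no exception, although it does order discontinuation for malignancy and anaphylaxis.

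Several narrower points stand:

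- The pointer to 4.2.1 is in the medical-reasons bullet, not the tuberculosis bullet. Other bullets also lack one, so its absence proves little by itself.
- Section 6.2.1 is worded as permission. It supports the stricter reading but does not expressly forbid anything.
- Tuberculosis infection is an adverse event of special interest, reportable within 24 hours (5.2.6.1.4 and 5.2.6.2.2), and a data monitoring committee reviews safety. The sponsor should therefore hear of a case early. This makes wrong re-dosing less likely but leaves the restart text in place.
- The 2.5-point figure holds for n = 40 and is not a ceiling. With an assumed 30 patients in the full analysis set, one patient is 1/30 = 3.3 points.
- Section 5.2.6.1.4 lists hepatitis B reactivation and hepatitis C progression as opportunistic infections, so 4.2.1 would let those restart too, while 3.3.4.1 discontinues for a positive hepatitis B or C test. This is a similar overlap.

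**Conclusion.** The concern holds. For active tuberculosis one section requires discontinuation and another permits restart, and nothing in the protocol decides between them. Its weight is in patient safety and consistent site conduct, not in the statistics.

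The size rests on an assumed 0 to 1 cases. Restart is open only if the infection is judged resolved within the 16-week (at most 20-week) gap, and the documents do not show how likely that is. One case would move an overall binary response rate by 2.5 points at n = 40 or 2.2 at n = 45, and more in a smaller analysis set. The primary endpoint is unchanged. Confidence is high in the textual conflict; the chance of actual re-dosing is unknown.

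**What to change.** In Section 4.2.1, take confirmed active tuberculosis out of the restart provision and state that it requires permanent discontinuation under Section 3.3.4.1. Leave latent tuberculosis under Section 6.2.1. Add a reference to Section 4.2.1 to the tuberculosis bullet in 3.3.4.1, as the malignancy bullet already has. If the clinical team does mean to allow restart, qualify the 3.3.4.1 bullet to say so. The hepatitis B and C overlap could be settled in the same edit.

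The cost is one sentence and one cross-reference, in the next protocol amendment or a clarification letter to sites. Data collection and analysis do not change.

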3.3.4.2 Withdrawal of consent to trial participation

Patients may withdraw their consent to trial participation at any time without the need to justify the decision.

If a patient wants to withdraw consent, the investigator should be involved in the discussion with the patient and explain the difference between trial treatment discontinuation and withdrawal of consent to trial participation, as well as explain the options for continued follow-up after trial treatment discontinuation, please see [Section 3.3.4.1](#) above.

3.3.4.3 Discontinuation of the trial by the sponsor

Boehringer Ingelheim reserves the right to discontinue the trial overall or at a particular trial site at any time for the following reasons:

1. Failure to meet expected enrolment goals overall or at a particular trial site.
2. Emergence of any efficacy/safety information invalidating the earlier positive benefit-risk-assessment that could significantly affect the continuation of the trial.
3. Deviations from GCP, the trial protocol, or the contract impairing the appropriate conduct of the trial.

The investigator / the trial site will be reimbursed for reasonable expenses incurred in case of trial termination (except in case of the third reason).

4. TREATMENTS

4.1 INVESTIGATIONAL TREATMENTS

4.1.1 Identity of the Investigational Medicinal Products

Table 4.1.1: 1 Test product

Substance:	BI 655130
Pharmaceutical formulation:	Solution for SC injection
Source:	BI Pharma GmbH & Co. KG, Biberach, Germany
Unit strength:	150mg/mL, 1mL prefilled syringe
Posology:	600mg once every 4 weeks
Method and route of administration:	Subcutaneous

4.1.2 Selection of doses in the trial and dose modifications

The dose selected for this extension trial is 600 mg SC every 4 weeks. The exposure from a single dose of 600 mg SC is expected to be approximately 60% of the 600 mg i.v. given in the parent trial. The rationale for this dose relates to the feasibility of administering more than 600 mg (4 x 1mL syringe) at a single visit. Thus, it is expected that 600 mg SC will be at or above the to-be-marketed dose. If the data from the non-treatment portion of the parent trial indicates that a different posology is efficacious, the trial will be updated with this new posology, i.e. every 6 or 8 weeks.

For the parent trial, a fixed rather than weight-based dose regimen of single dose of 600 mg was selected. Early trials of therapeutic monoclonal antibodies often investigate body-weight-based regimens to reduce the inter-subject variability in drug exposure. However, there is generally only a modest contribution of body weight to the overall pharmacokinetic (PK) and pharmacodynamic (PD) variability of monoclonal antibodies. Furthermore, monoclonal antibodies are highly target specific and offer a relatively large therapeutic window compared to new chemical entities. Therefore, most monoclonal antibodies are approved at fixed doses in antibody/target excess in order to cover target turnover and maximize efficacy [[R10-6267](#); [R13-4749](#); [R13-4753](#); [R13-4750](#); [R13-4754](#)].

